### **5.7. Safety Set**

#### Safety Set (Part 2, Cross-Over Subjects)

Safety Set (Part 2, Cross-Over Subjects) consists of all participants from Part 2 placebo group who cross over and receive mRNA-1273 in open-label phase.

#### Safety Set (Long-term Analysis)

The Safety Set (Long-term Analysis) consists of Safety Set (Part 2, Cross-Over Subjects) for Placebo-mRNA-1273 group and Safety Set for mRNA-1273 group. The Safety Set for Long-term Analysis for mRNA-1273 group is same as the Safety Set in Part 1 open-label phase and Part 2 blinded phase. The Safety Set will be used for analysis of safety except for the solicited ARs. Participants will be analyzed in the mRNA-1273 group or Placebo-mRNA-1273 group.

#### Safety Set (Part 3, First Two Doses of Primary Series)

The Safety Set of Part 3, first two doses of primary series consists of all enrolled participants who received any study injection. The Safety Set will be used for analysis of safety except for the solicited ARs. In addition, the following Safety Set is defined for each injection separately. The First (Second) Injection Safety Set consists of all subjects in the Safety Set who have received the first (second) study injection. Participants will be included in the vaccination group corresponding to the vaccination they actually received.

#### Safety Set (Booster/Third Dose Analysis)

The Safety Set in Booster/Third Dose Analysis consists of all participants who received a booster/third dose in booster/third dose analysis phase. The Safety Set will be used for analysis of safety except for the solicited ARs. Participants will be analyzed according to their treatment group (mRNA-1273-mRNA-1273 Booster/mRNA-1273.214 Booster or Placebo-mRNA-1273- mRNA-1273 Booster/mRNA-1273.214 Booster for booster dose analysis and mRNA-1273-Third Dose for third dose analysis).

For mRNA-1273- mRNA-1273 Booster/Third Dose treatment group, participants from the Part 1 or Part 3 open-label phase or the Part 2 blinded phase mRNA-1273 group in primary series who received booster/third dose of mRNA-1273 are included.

For Placebo-mRNA-1273-mRNA-1273 Booster treatment group, participants from the Part 2 blinded phase placebo group who crossed over to mRNA-1273 after unblinding and received a booster dose of mRNA-1273 are included.

For mRNA-1273- mRNA-1273.214 Booster treatment group, participants from the Part 1 open-label phase or the Part 2 blinded phase mRNA-1273 group in primary series who received a booster dose of mRNA-1273.214 are included.

For Placebo-mRNA-1273-mRNA-1273.214 Booster treatment group, participants from the Part 2 blinded phase placebo group who crossed over to mRNA-1273 after unblinding and received a booster dose of mRNA-1273.214 are included.

## **6. Statistical Analysis**

Unless specified otherwise, the Part 3 statistical analysis for the first two doses open-label phase and third dose phase will be similar to the analysis for primary series (refer to the SAP for Part 1 Open-Label Phase and Part 2 Blinded Phase) and booster analysis in Part 1 and Part 2 respectively.

## 6.1. General Considerations

The Schedule of Assessments is provided in [Appendix E](#) for Part 2 open-label phase and [Appendix F](#) for Booster dose analysis, and [Appendix H](#) for Part 3 .

**Continuous variables** will be summarized using the following descriptive summary statistics: the number of subjects (n), mean, standard deviation (SD), median, minimum (min), and maximum (max).

**Categorical variables** will be summarized using counts and percentages.

### Baseline Value for specific study phase

- **Part 2 pre-crossover:** unless specified otherwise, is defined as the most recent non-missing measurement (scheduled or unscheduled) collected before the first dose of mRNA-1273 in Part 2
- **Pre-booster/third dose:** unless specified otherwise, is defined as the most recent non-missing measurement (scheduled or unscheduled) collected before the booster/third dose

For the summary statistics of all numerical variables unless otherwise specified, the display precision will follow programming standards. Please see [Appendix A](#) for variable display standards.

When count data are presented, the percentage will be suppressed when the count is zero in order to draw attention to the non-zero counts. A row denoted “Missing” will be included in count tabulations where specified on the shells to account for dropouts and missing values. The denominator for all percentages will be the number of subjects in that vaccination group within the analysis set of interest, unless otherwise specified.

### Baseline SARS-CoV-2 Status:

- Baseline SARS-CoV-2 status for long-term analysis is determined by using virologic and serologic evidence of SARS-CoV-2 infection at the date of first mRNA-1273 (first dose of mRNA-1273 in the blinded phase or crossover first dose of mRNA-1273 in the open label). Negative SARS-CoV-2 status for long-term analysis is defined as a most recent negative RT-PCR test for SARS-CoV-2 and a most recent negative serology test based on bAb specific to SARS-CoV-2 nucleocapsid (as measured by Roche Elecsys Anti-SARS-CoV-2 assay) at the date of the first mRNA-1273 dose.

Positive SARS-CoV-2 status for long-term analysis is defined as a most recent positive RT-PCR test for SARS-CoV-2 at the date of the first mRNA-1273 dose, and/or a most recent positive serology test based on bAb specific to SARS-CoV-2 nucleocapsid (as measured by Roche Elecsys Anti-SARS-CoV-2 assay) at the date of the first mRNA-1273 dose.

- **Pre-booster/third dose SARS-CoV-2 Status**

Pre-booster/third dose SARS-CoV-2 status is determined by using virologic and serologic evidence of SARS-CoV-2 infection at the date of booster/third dose (BD-Day 1).

Pre-booster/third dose negative status is defined as a negative RT-PCR test for SARS-CoV-2 and a negative serology test based on bAb specific to SARS-CoV-2 nucleocapsid (as measured by Roche Elecsys Anti-SARS-CoV-2 assay) at the date of booster/third dose.

Else, Pre-booster/third dose positive SARS-CoV-2 status is defined as a positive RT-PCR test for SARS-CoV-2 at the date of booster/third dose, and/or a positive serology test based on bAb specific to SARS-CoV-2 nucleocapsid (as measured by Roche Elecsys Anti-SARS-CoV-2 assay) at the date of booster/third dose.

**Study day relative to the first injection in Part 2 open-label phase** will be calculated as below:

- a) study day prior to the first injection will be calculated as: date of assessment/event – date of the first injection of mRNA-1273 in Part 2 open-label phase (Crossover Day 1);
- b) study day on or after the date of the first injection will be calculated as: date of assessment/event – date of the first injection of mRNA-1273 in Part 2 open-label phase (Crossover Day 1) + 1;

**Study day relative to the injection in booster/third dose analysis** will be calculated as below:

- a) study day prior to the booster/third dose will be calculated as: date of assessment/event – date of the injection in booster/third dose analysis;
- b) study day on or after the date of the booster/third dose will be calculated as: date of assessment/event – date of the injection in booster/third dose analysis + 1;

**Study day relative to the most recent injection** will be calculated as below:

- a) study day on or after the date of the first injection in Part 2 open-label phase (if applicable) but before the second injection in Part 2 open-label phase (if applicable) will be calculated as: date of assessment/event – date of the first injection of mRNA-1273 in Part 2 open-label phase + 1;
- b) study day on or after the date of the second injection in Part 2 open-label phase (if applicable) but before the injection in booster dose analysis (if applicable) will be calculated as: date of assessment/event – date of the second injection of mRNA-1273 in Part 2 open-label phase + 1;
- c) study day on or after the date of booster/third dose analysis (if applicable) will be calculated as: date of assessment/event – date of the injection in booster/third dose analysis + 1;  
if study day is on the same day as the injection, date and time will be compared with the injection date and time.

**For calculation regarding antibody values in booster/third dose analysis**, antibody values reported as below LLOQ will be replaced by  $0.5 \times \text{LLOQ}$ . Values that are greater than the upper limit of quantification (ULOQ) will be converted to the ULOQ if actual values are not available, and actual values will be used if available. Missing results will not be imputed.

The following analysis periods for Long-term and booster/third dose phase safety analyses will be used as applicable for specific subjects group in this study:

- Up to 28 days after any vaccination (mRNA-1273 primary series or booster/third dose): this stage starts at the day of each vaccination and continue through the earliest date of (the day of each vaccination and 27 subsequent days, next vaccination [if applicable]). This analysis period will be used as the primary analysis period for safety analyses including unsolicited AE, except for solicited AR, unless specified otherwise.
- Overall period or throughout the study: this analysis period starts at the first injection on Day 1 and continues through the earliest date of (study completion, discontinuation from the study, or death).

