#### **4.4. Blinding and Unblinding**

This study is conducted in three parts, Part 1 of this study will be open label, blinding procedures will not be applicable.

Part 2 of this study will be conducted in an observer-blind manner. The investigator, study staff, study participants, study site monitors, and Sponsor personnel (or its designees) will be blinded to the IP administered until study end, with certain exceptions, please refer to Section 8.1 of the protocol for details.

Part 3 is open label; however, if blinded administration is ongoing at the site, blinded procedure for Part 2 still applies.

The final analysis of all endpoints will be performed after all participants have completed all planned study procedures.

At the time of interim analysis, only pre-identified Sponsor and unblinded Contract Research Organization (CRO) team members as specified in the study Data Blinding Plan will be unblinded to review treatment level results and individual listings. Please also refer to [Section 6.9](#). Study sites will remain blinded to individual treatment assignments until the end of the study.

If a COVID-19 vaccine is authorized or licensed for a specific age group before the end of the study, please refer to protocol section 3.3 for unblinding and/or cross-over plans.

Participants under 6 years of age in Part 2 who have reached at least 6 months follow up after Dose 2 will be eligible for unblinding via a telephone call to learn which treatment they received. Participants who received placebo will be offered the option of cross-over vaccination with mRNA-1273 at that point as described above.

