### **3. Study Endpoints**

#### **3.1. Part 2, Open-label Phase**

The study endpoints in Part 2 open-label phase are same as Part 2 blinded phase. Please refer to section 3 in Part 1 open-label phase and Part 2 blinded phase SAP.

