## **5.2. Immunogenicity Subset**

### Immunogenicity Subset (Long-term Analysis)

Immunogenicity Subset for long-term analysis at Day 1, Day 57 and Day 209 consists of

- a) a subset of participants in the FAS (Long-term Analysis) and
- b) have baseline (pre-dose 1 of mRNA-1273) SARS-CoV-2 status available, and
- c) have baseline (pre-dose 1 of mRNA-1273) and at least one post-injection antibody assessment for the analysis endpoint.

Immunogenicity Subset for long-term analysis only includes subjects who received mRNA-1273 in Part 1 open-label phase and Part 2 blinded and open-label phase.

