## 5.5. Modified Intent-to-Treat-1 (mITT1) Set

### mITT1 Set (Part 2, Cross-Over Subjects)

mITT1 Set (Part 2 Cross-Over Subjects) for placebo-mRNA-1273 group consists of all cross-over participants who were previously included in the mITT1 set for the Part 2 blinded phase analysis and in the FAS (Part 2, Cross-Over Subjects) who had no serologic or virologic evidence of prior SARS-CoV-2 infection (no positive RT-PCR test and no positive serology test based on bAb specific to SARS-CoV-2 nucleocapsid) on or before the date of the first cross-over mRNA-1273 dose in open-label phase and received at least one dose of mRNA-1273 without wrong treatment, i.e., all FAS cross-over participants excluding those with positive or missing RT-PCR test or serology test prior to the first dose of mRNA-1273 and those who received the wrong treatment in open-label phase (i.e., at least one dose received in open-label phase is not as assigned).

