#### **8.5. Appendix E: Schedule of Assessments for Placebo Recipient Cross-Over Vaccination with mRNA-1273 if any COVID-19 Vaccine is Authorized or Licensed for Participant's Age Group**

| Schedule of Assessments for Placebo Recipient Cross-Over Vaccination                 | Cross-Over D1 | D29 (+ 7) | D36 (+ 3) | D57 (+ 7) | Remainder of Study Visits |
|---|----------------------|------------------------------|------------------|------------------|----------------------------------|
| Days Since Most Recent Injection   |                      | 28                           | 7                | 28               |                                  |
| Study injection (including 30-minute post-dose observation period)                          | X                    | X                            |                  |                  |                                  |
| Safety follow-up call   |                      |                              | X                | X                |                                  |
| Pregnancy test    | X                    | X                            |                  |                  |                                  |
| Recording of unsolicited AEs  | X                    | X                            | X                | X                |                                  |
| Recording of MAAEs and concomitant medications relevant to or for the treatment of the MAAE | X                    | X                            | X                | X                | X                                |
| Recording of SAEs and concomitant medications relevant to or for the treatment of the SAE   | X                    | X                            | X                | X                | X                                |
| Recording of AESIs (eg, MIS-C and myocarditis and/or pericarditis)                          | X                    | X                            | X                | X                | X                                |

Abbreviations: AE = adverse event; AESI = adverse event of special interest; COVID-19 = coronavirus disease 2019; D = day; MAAE = medically attended adverse event; MIS-C = multisystem inflammatory syndrome in children; SAE = serious adverse event.

1. Authorized or licensed in participant's age group.

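### Nucleocapsid status of placebo crossovers is carried forward with no age limit, so blinded-phase infections can be mislabelled or dated as post-mRNA-1273 cases

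*SAP*

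**What the plan says.** The document holds two plans: one for Part 1 and the Part 2 blinded phase (the blinded-phase SAP) and one for the Part 2 open-label phase, boosters and Part 3 (the open-label/booster SAP). Each has its own Appendix E. Unless stated otherwise, the sections below are in the open-label/booster SAP.

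- **Schedule.** Section 6.1 states: "The Schedule of Assessments is provided in [Appendix E](#) for Part 2 open-label phase". That appendix is headed "Schedule of Assessments for Placebo Recipient Cross-Over Vaccination with mRNA-1273 if any COVID-19 Vaccine is Authorized". Its rows are injections, safety calls, pregnancy tests and recording of adverse events.
- **Status rule.** Section 6.1 fixes long-term baseline status for the Placebo-mRNA-1273 group at the "crossover first dose of mRNA-1273 in the open label", from the most recent RT-PCR and the most recent nucleocapsid serology. No maximum age is given. Criterion (d) of the long-term PP Immunogenicity Subset (Section 5.3) requires a negative status at that point.
- **Crossover mITT1 Set (Section 5.5).** This set has its own rule. It requires prior membership of the blinded-phase mITT1 Set and no positive test up to the first crossover dose, "excluding those with positive or missing RT-PCR test or serology test prior to the first dose of mRNA-1273".
- **Long-term Immunogenicity Subset (Section 5.2).** Members must "have baseline (pre-dose 1 of mRNA-1273) and at least one post-injection antibody assessment for the analysis endpoint", and open-label mRNA-1273 recipients are included.
- **Timing.** Section 4.4 of the blinded-phase SAP makes eligible for unblinding "Participants under 6 years of age in Part 2 who have reached at least 6 months follow up after Dose 2".
- **Endpoints.** Section 3.1: "The study endpoints in Part 2 open-label phase are same as Part 2 blinded phase". Section 3.1 of the blinded-phase SAP names the Part 2 open-label phase for both solicited reactions and Day 57 immunogenicity.

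**The concern.** A baseline tied to the first crossover dose suggests that infection status is known at that moment. The crossover schedule collects nothing that would establish it, so the plan falls back on whatever the blinded phase left behind. For most placebo children the serological part of that is the Day 1 sample.

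Two results depend on it: who counts as previously uninfected in the long-term immunogenicity analysis, and whether a seroconversion found after crossover is attributed to the period before or after mRNA-1273. By contrast, the mRNA-1273 booster schedule (Appendix F) does collect blood and a swab on BD-Day 1.

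**Working it through.** The plan gives no figure for this point, so the check is a row-by-row reading plus counts from Table 2 of the blinded-phase SAP. As a check on those counts, 3 × 176 = 528 children, or 3 × 132 = 396 on mRNA-1273 and 3 × 44 = 132 on placebo. This matches Section 4.2 of the blinded-phase SAP.

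**1. What crossover collects.** Appendix E has no swab, blood or eDiary row at Cross-Over D1, D29, D36 or D57. The column for remaining visits is ticked only for MAAEs, SAEs and AESIs.

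**2. Who has only Day 1 serology.** The placebo arm is up to 1,000 per age group.
- Cohorts A, B, C and E: 3 × 44 + 6 = 138.
- Cohort D: 1,000 − 138 = 862 (86.2%). Its Day 30 tube is stored for possible biomarker work.
- Assuming smaller arms: (750 − 138)/750 = 81.6%; (500 − 138)/500 = 72.4%.
- Cohorts A and C, last drawn at Day 57 before a crossover near Day 209: 88 (8.8%).
- Cohorts B and E, with a Day 209 draw: 50 (5.0%).

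**3. Age of the result (under 6 years).** Dose 2 falls on Day 29 and the 6-month visit 180 days later: 29 + 180 = Day 209.
- Cohort D: 209 − 1 = 208 days or more.
- Cohorts A and C: 209 − 57 = 152 days or more.
- RT-PCR differs: the blinded-phase schedule has swabs at Days 29, 57 and 209 that are not restricted by cohort, so a crossover near Day 209 can have a current RT-PCR result.

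**4. Consequence (a): two rules, two answers.** Take a Cohort D placebo child with negative Day 1 serology, a positive RT-PCR during the blinded phase and a negative swab later.
- Section 6.1: most recent RT-PCR negative, most recent serology negative, so status is negative. Criterion (d) of the long-term PP set is met.
- Section 5.5: a positive RT-PCR before crossover, so the child is excluded from the crossover mITT1 Set.

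To enter the PP set the child also needs a post-injection antibody value, which limits how many are affected.

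**5. Consequence (b): misdated infection.** Take a placebo child silently infected in the blinded phase and missed by every swab. With no positive test on record, the child passes both rules. Section 6.5.1.1 dates an infection by its first positive test and counts it from 14 days after the second mRNA-1273 injection. It can surface by two routes:
- *Ages 6 to <12, BD-Day 1.* Appendix G draws blood at BD-Day 1 in every Part 2 sub-cohort. Appendix F puts the booster at least 6 months after Dose 2, so the 14-day condition is met. The until-booster efficacy period in Section 6.1 includes the booster date. The infection is counted as post-mRNA-1273.
- *Day 394, Cohorts C and E.* 44 + 6 = 50 placebo children per age group, if blinded-phase draws continue after crossover. For a crossover at Day 209, counting starts at Day 209 + 28 + 14 = Day 251, before Day 394. Cohort E has a Day 209 sample, so it is exposed only to infection after that draw.

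Section 6.5 stops incidence calculation after October 2022, which removes later draws from both routes.

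**6. Endpoints against collection.** Section 5.6 defines Solicited Safety Sets only for Part 3 and for booster or third dose. Section 6.3.2 analyses solicited reactions only after booster or third dose. Table 4 in Appendix B has no crossover visit windows. Appendix E has no Day 57 draw.

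**The case against.** The strongest reply is that the plan never demands a same-day test. It carries the last result forward by rule, and a Day 1 blood sample is a condition of entry, so data are old rather than absent. Scheduled swabs and symptom surveillance during the blinded phase leave only infections missed by both. All of this stands. It does not cure the missing age limit on serology or the dating rule.

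A reader might infer that the crossover mITT1 Set, and hence the incidence analysis, rests on the most-recent rule. It does not: Section 5.5 already applies a cumulative no-prior-positive rule and excludes missing results. Consequence (a) therefore concerns the PP long-term set. Consequence (b) survives because a silent infection leaves no earlier positive.

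A reader might also multiply 862 by an infection rate; an assumed 5% to 20% gives 43 to 172 children. The documents give no rate. The product also assumes full enrolment, full uptake of an optional crossover and no detection by swab. It is illustrative only.

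Finally, the protocol is not at hand. The blinded-phase SAP mentions a Participant Decision Visit that Appendix E does not list, and sampling there cannot be ruled out.

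**Conclusion.** The point holds in a limited form. Status at crossover rests on carried-forward serology with no age limit. For up to 862 of 1,000 placebo children per age group, that serology is the Day 1 sample. The figure of 208 days or more applies to under-6s crossing over at or after six months from Dose 2; timing for ages 6 to <12 is left to the protocol. Followed as written, the rules can label a known earlier infection as negative in the PP long-term set and can count a blinded-phase infection as a post-mRNA-1273 case.

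No net direction of bias is shown. Misdated seroconversions raise serology-based incidence, while undetected prior immunity would lower symptomatic incidence. Solicited reactions classify no one; their listing, like that of Day 57 immunogenicity, is an endpoint-list inconsistency. It would be wrong to infer a threat to the primary noninferiority tests: Sections 2.1 and 6.5 make these analyses descriptive or exploratory. The change is still worth making because it is specific and cheap.

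**What to change.** No new procedures are needed. In the open-label/booster SAP:

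1. Align the status rule in Section 6.1 and criterion (d) of the long-term PP set with the cumulative no-prior-positive rule of the crossover mITT1 Set.
2. For the Placebo-mRNA-1273 group, make RT-PCR-confirmed COVID-19 the incidence result. Count serology-only infections only where a negative nucleocapsid result close to crossover exists, with the permitted interval stated and justified. Report the all-serology count as a sensitivity analysis.
3. Tabulate the time from last serology to first crossover dose, by age group and cohort.
4. Show this group's long-term antibody results only with time since crossover dose, and omit them where there is no draw both before and after crossover.
5. Limit the open-label endpoint list to what Appendix E collects. If the protocol adds crossover sampling, reconcile Appendix E with it instead.

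The cost is SAP wording, one table and the loss of some serology-only cases from an exploratory analysis.
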